1.0 Background

Diabetes is a leading cause of cardiovascular disease, renal failure, vision loss and non-traumatic lower limb amputations. Diabetes self-management can prevent or delay diabetes-related complications, yet patients struggle to consistently engage in recommended self-care behaviors. Patients with diabetes may lack the understanding and motivation necessary to successfully manage their disease. Among patients with diabetes, studies have found that higher patient activation (i.e., knowledge, skills and confidence to manage their own health and care) is associated with healthy eating, blood sugars monitoring, eye exams and immunizations. Many of these findings were reported in diverse and disadvantaged populations.

Patient portals offer a vehicle for interventions aimed at increasing patient activation, improving understanding, and promoting self-management, while overcoming the limitations of costly and difficult to scale face-to-face programs. We recently applied user-centered design sprint methodology and key strategies for patient engagement to develop a multi-faceted patient portal intervention, My Diabetes Care (MDC), designed to help patients better understand their diabetes health data as well as support self-management. MDC was embedded within an established patient portal on Epic's MyChart platform and best viewed on mobile devices. MDC uses infographics to visualize and summarize patients' diabetes health data and provides literacy-level appropriate educational and self-management resources. MDC is grounded in a well-established Chronic Care Model (CCM) adapted for eHealth (i.e., healthcare practices supported by electronic processes and communication). By leveraging elements within the Model's five domains (self-management support, delivery system design, decision support, clinical information systems, and eHealth education), MDC has the potential to create more informed and activated patients leading to improved outcomes.

2.0 Rationale and Specific Aims

To demonstrate scalability and assess usage patterns, user experience, and to uncover errors in functionality at two study sites prior to a larger randomized trial (to be proposed separately), we will conduct a scalability and usability study MDC. The study will utilize questionnaires to quantify participants' perceptions and responses to the MDC and semi-structured interviews to comprehensively assess users' experience, barriers to use, and reasons for non-use or discontinued use. Combining qualitative and quantitative assessments of usability identifies more usability concerns than quantitative (e.g., questionnaires) assessments alone. Each participant will have access to the MDC for 1 month from the time of enrollment. This duration allows sufficient time for participants to become familiar with MDC and determine if and how to use MDC in the management of their diabetes.

3.0 Inclusion/Exclusion Criteria

Participants will be eligible for the study if they have T2DM, currently taking at least one medication for diabetes, are able to speak and read in English or Spanish, are age 18 to 75, have reliable access to a smartphone or tablet with internet access and have a patient portal account at a participating site (i.e., a Patient Gateway account at Brigham & Women's Hospital (BWH) or a My Health at Vanderbilt account at Vanderbilt University Medical Center (VUMC)).

We will exclude patients with a medical condition that affects their memory or ability to think, severe visual or hearing impairment, or a medical condition that make it hard for people to understand what they are saying (e.g., dysarthria).

4.0 Enrollment/Randomization

Participants will be able to complete an electronic consent form and enroll online via Research Electronic Data Capture (REDCap™) version 5.0.8.

5.0 Study Procedures

Setting. The study will be conducted at two sites: (1) the VUMC Primary Care (including Shade Tree Clinic) and Diabetes clinics located throughout the greater Nashville, TN area, and (2) the BWH Primary Care clinics located throughout the greater Boston, MA area. At both sites, an electronic health record (EHR) from Epic Systems Corp. stores all clinical data and patients receive access to their clinical data via an integrated patient web portal that is accessible on desktops and via a native mobile app for iOS and Android mobile operating systems.

Participants and Recruitment. At VUMC, potential participants will be identified automatically using VUMC's Subject Locator to query the EHR for patients with upcoming clinic appointments who meet the discrete inclusion and exclusion

criteria. In addition, we will use EHR-based recruitment. We will use a Custom Reporting Workbench Report to identify established adult patients with type 2 diabetes who receive care at participating clinics. These patients are the target population for study (i.e., Vanderbilt primary care patients with diabetes) and as such these patients are potentially eligible to participate in the study.

At BWH, potential participants will be identified using a similar EHR-based recruitment strategy. The BWH EHR will be queried to identify patients that meet the eligibility criteria.

With permission of the clinic directors at both sites, potentially eligible patients, will be mailed a recruitment letter describing the study and providing contact information for IRB approved study personnel. If after receiving the letter, a patient is interested in the study, the patient may contact study personnel to learn more and consider participating in the study. The recruitment letter will include a QR code and URL link to the eligibility screener in REDCap. After reviewing the study eligibility criteria on the REDCap pre-screener, interested patients who believe they are eligible can advance to the REDCap Informed Consent Document (ICD). Participants will complete a self-administered electronic consent form and enroll online via REDCap. Participants may have one or more of these characteristics. Study staff will be available to answer questions of potential participants during the consent process and will also review the ICD and study participation with all patients who enroll. Patients who do not respond to the recruitment letter may be contacted by phone to ensure they received the letter and offer them information about the study.

In addition, we will distribute study flyers to participating clinic sites. As with the recruitment letter, the study flyer will include the QR code and URL link to the eligibility pre-screener in REDCap where interested patients can review eligibility criteria, review the consent form, and enroll. If a patient is interested in the study, they may contact study personnel to learn more and consider participating in the study. Contact information (study phone number and e-mail address) is included on the study flyer and throughout the REDCap process. In accordance with best practices and to reflect a range of patient experience with diabetes and groups with distinct usability needs, we will use oversampling and purposive sampling with the aim of achieving approximately 25% or more representation of each of the following characteristics: (a) limited health literacy and (b) age 65 or over, and 40% or more racial and ethnic minorities.

Data Collection and Outcome Measures. Study participants will complete questionnaires electronically via email using REDCap™ at two time points: enrollment (T₀) and end of study (T₁). Participants will complete an enrollment questionnaire (T₀) including basic demographic questions, items about computer usage and internet access, and validated measures of health literacy, numeracy, and eHealth literacy.

The primary outcome measures (**Table 1**) will be: (a) ease of use and satisfaction as assessed by the System Usability Scale at T₁, (b) system usage data as assessed by MDC user analytics at T₁, (c) user experience as assessed by end of study questionnaire and semi-structured interviews at T₁. In addition, we will assess pre/post change in the following secondary cognitive and behavioral outcomes (Table 1) to estimate effect size and standard deviations for power analyses necessary to plan a subsequent randomized controlled trial to be proposed in a subsequent IRB application.

Table 1. Outcome Measures

Primary Outcomes	Measures	Variable Type	How Collected	Time Point
Usability	System Usability Scale	Continuous	Questionnaire	T ₁
System usage data	Number of MDC visits	Continuous and categorical	System analytics (if available), self-report	T ₁
User experience	Unique study specific items to assess participants' perspectives on content, layout, acceptance, and particular features and functionality	Categorical, Qualitative	Questionnaire, Interviews	T ₁
Secondary Cognitive/Behavioral Outcomes				
Diabetes knowledge	Revised Brief Diabetes Knowledge Test (DKT2)	Continuous	Questionnaire	T ₀ and T ₁
Diet adherence	Summary of Diabetes Self-Care Activities (SDSCA) – Diet Subscale	Continuous	Questionnaire	T ₀ and T ₁
Exercise adherence	SDSCA – Exercise Subscale	Continuous	Questionnaire	T ₀ and T ₁
Glucose self-monitoring adherence	SDSCA – Self-monitoring of Blood Glucose Subscale	Continuous	Questionnaire	T ₀ and T ₁
Medication adherence	Adherence to Refills and Medications Scale (ARMS)	Continuous	Questionnaire	T ₀ and T ₁
Diabetes self-efficacy	Perceived Diabetes Self-Management Scale (PDSMS)	Continuous	Questionnaire	T ₀ and T ₁
Diabetes distress	Problem Areas in Diabetes Scale (PAID)-5	Continuous	Questionnaire	T ₀ and T ₁

Knowledge of Diabetes Measures	Unique study specific items to assess participants' knowledge of measures of diabetes health status	Categorical	Questionnaire	T ₀ and T ₁
Diabetes Readiness for Change	Four items assessment resources to assess stage of change based on the Transtheoretical Model (TTM) of behavior change. It includes questions on physical activity, medication management, glucose self-monitoring, and diet.	Categorical	Questionnaire	T ₀ and T ₁

Based on pilot testing, we estimate time to completion for questionnaires to be 20 minutes at T₀ and T₁. Participants will be compensated \$40 for completing the enrollment questionnaire, \$35 for completing the study end questionnaire, and \$5 for first 10 minutes of MDC use during which participants will be encouraged to familiarize themselves with the full functionality of the MDC.

At the conclusion of their one month of MDC access, we will conduct one-on-one, semi-structured interviews with a subsample of participants including participants from each of the purposively sampled groups (see *Recruitment* above). This methodology is most appropriate for in-depth assessment of patients' perceptions and reactions regarding a proposed intervention. Interviews are preferred over focus groups for understanding usability because focus groups can amplify bias and individual opinions. Interviews will take place by phone or via Zoom after concluding their one month of MDC access. Interviews will last approximately 30-40 minutes. A trained interviewer will use a semi-structured interview guide to facilitate the interview and elicit in-depth understanding of participants' perceptions and experiences with specific MDC functionality as well as barriers to use, and reasons for non-use or discontinued use. Additional participants will be interviewed until saturation is reached. Saturation will be defined as no new usability concerns raised in the preceding two interviews and typically occurs between 10 and 30 interviews. Participants will be compensated an additional \$40 for the interview.

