6.0 Statistical Analysis Plan

We will use descriptive statistics to characterize the study participants and survey data. We will use a one sample t-test to compare the mean SUS score at T1 to the threshold score of 71 indicative of "good" usability. If the distributions of SUS scores suggest asymmetry or nonnormality, the non-parametric sign test (highly asymmetrical) or Wilcoxon signed-rank test (non-normality) will be performed in lieu of one-sample t-tests. To assess whether there was a significant improvement in the continuous secondary cognitive/behavioral outcomes from baseline to end of study (T₀ to T₁), we will perform two-sided paired t-tests on the pairwise differences. If any of the distributions of pairwise differences suggest asymmetry or nonnormality, the non-parametric Wilcoxon signed-rank sum test will be performed in lieu of paired t-tests. We will use the McNemar's test for to compare paired proportions.

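### Does oversampling three groups with distinct usability needs oblige the plan to prespecify a System Usability Scale (SUS) result for each group?

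*Combined protocol and SAP*

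**What the plan says.** Section 5.0, Participants and Recruitment, gives the reason for the sampling scheme: to "reflect a range of patient experience with diabetes and groups with distinct usability needs, we will use oversampling and purposive sampling". It aims for "approximately 25% or more representation of each of the following characteristics", namely limited health literacy and age 65 or over, and for 40% or more racial and ethnic minorities. The same section states "Participants may have one or more of these characteristics". That sentence stands before the list and follows one about consent, so reading it as a remark on overlapping groups is plausible but inferred.

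Under Data Collection and Outcome Measures, the baseline questionnaire covers demographics and "validated measures of health literacy, numeracy, and eHealth literacy". The SUS at end of study is a primary outcome. The interview paragraph plans "semi-structured interviews with a subsample of participants including participants from each of the purposively sampled groups".

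Section 6.0 contains two sentences that bear on the SUS. One is general: "We will use descriptive statistics to characterize the study participants and survey data". The other is the test: "We will use a one sample t-test to compare the mean SUS score at T1 to the threshold score of 71". If the scores are skewed or non-normal, "the non-parametric sign test (highly asymmetrical) or Wilcoxon signed-rank test (non-normality) will be performed in lieu of one-sample t-tests". These fallbacks are also pooled. Nothing in section 6.0 mentions health literacy, age or race and ethnicity.

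**The concern.** The protocol goes out of its way to enrol three kinds of patient because their usability needs may differ, yet the one SUS analysis it specifies averages over them. Two consequences suggest themselves.

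- **Masking.** A pooled mean at or above 71 can coexist with an oversampled group below 71, and a reader of the pooled result alone would not see it.
- **Dependence on mix.** The recruitment targets are floors without ceilings, so the pooled mean depends partly on how far each floor is exceeded.

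A shortfall in one group would matter to a study meant to find problems before a larger randomised trial. If group figures were produced only after the data had been seen, the choice of which to show could be selective.

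**Working it through.** The plan states no sample size, SUS SD, expected mean or significance level for the SUS test, so there is no planned figure to reproduce. From the documents come the threshold of 71 and the target shares of 25% and 40%. Assumed for illustration: 80 participants in all, SD 18 (range 12 to 22), a group mean of 65, and a two-sided 5% level.

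**1. Masking of the pooled mean (needs no sample size or SD).** Let a group with share p average d below 71 and the rest average x above it. The pooled mean is 71 when p(71 − d) + (1 − p)(71 + x) = 71, so x = d·p/(1 − p).
- p = 0.25: x = d/3. A group at 65 (d = 6) is offset if the rest average 73.
- p = 0.40: x = 2d/3. A group at 65 is offset if the rest average 75.

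**2. Masking behind a significant result.** With n = 80 the observed mean must reach c = 71 + t(0.975, 79)·SD/√80. This is 73.67, 75.01 and 75.90 for SD 12, 18 and 22. With the group at 65 the rest must average (c − p·65)/(1 − p).

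| Share | SD 12 | SD 18 | SD 22 |
|---|---|---|---|
| 25% | 76.6 | 78.3 | 79.5 |
| 40% | 79.5 | 81.7 | 83.2 |

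The gap between group and rest therefore has to run from 76.6 − 65 = 11.6 to 83.2 − 65 = 18.2 points. Nothing in the documents suggests a gap of that size.

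**3. Dependence on mix.** If the group scores g below the rest, raising its share from 25% to 40% lowers the pooled mean by 0.15g. With 65 and 74 (g = 9):
- 0.25·65 + 0.75·74 = 71.75
- 0.40·65 + 0.60·74 = 70.40

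The shift is 1.35 points, against a pooled 95% half-width of t(0.975, 79)·18/√80 = 4.0.

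**4. What a table by group would show.** The 95% half-width is t(0.975, n − 1)·SD/√n.

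| Group n | SD 12 | SD 18 | SD 22 |
|---|---|---|---|
| 10 | 8.6 | 12.9 | 15.7 |
| 20 | 5.6 | 8.4 | 10.3 |
| 30 | 4.5 | 6.7 | 8.2 |

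A quarter of 80 is 20. For 20 people with mean 65 the interval is 56.6 to 73.4 at SD 18, which includes 71. At SD 12 the upper limit is 65 + 5.6 = 70.6, which excludes it. Whether a group estimate would be informative thus turns on an n and SD that the documents do not give.

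**5. The text side by side.** The sampling passage speaks of reflecting a range of patients and promises no comparison between them. Section 2.0 states aims of usage, experience and functional errors, again without a group contrast. The interview paragraph draws on every oversampled group. The descriptive sentence in section 6.0 covers survey data, and the SUS is survey data, so a breakdown is allowed though not promised. The grouping variables are already collected at baseline.

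**The case for a change.** The best argument for a change is that the protocol itself names these groups as having distinct usability needs. A sentence that merely permits a table does not commit anyone to producing it. Section 2.0 argues that qualitative and quantitative assessment together find more usability concerns than questionnaires alone, yet by group only the interviews are planned. The remedy would be cheap: one paragraph and one table, with no new data. Wide intervals shown openly tell a reader more than no figure.

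Much of this is true. Section 6.0 does not commit to SUS by group, and the table would be useful. The measure and cut-off for limited health literacy are also not stated, though checking the 25% recruitment target requires them in any case.

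What does not stand is the step from a useful addition to a defect. The groups have a planned use in the interviews, so the oversampling is not idle. The scope for selective choice is small: the three characteristics are named before any data are collected, and the age boundary is fixed at 65. What remains open is mainly the health-literacy cut-off and the coding of minority status. No subgroup claim is planned that a selective choice could distort.

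**Conclusion.** No change to the plan is needed. The pooled comparison with 71 answers a clear question about the sample as enrolled, and no stated aim goes unmet without SUS results by group. This is a gap that analysts can fill sensibly under the descriptive sentence, from data already collected, by describing each characteristic separately and without tests.

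The possible harm is modest and wholly conditional. Offsetting a low group in the pooled mean is easy arithmetically (d/3 at a 25% share, 2d/3 at 40%). Hiding it behind a significantly favourable result takes a gap of roughly 12 to 18 points under the assumed 80 participants, SD 12 to 22 and group mean of 65. The mix effect in the example, 1.35 points, is well inside the pooled half-width of 4.0. Group estimates would probably be imprecise, about 8.4 points either side at an assumed 20 people and SD 18. They would not be uninformative in every case, since at SD 12 a group averaging 65 would exclude 71.

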6.0 Statistical Analysis Plan

We will use descriptive statistics to characterize the study participants and survey data. We will use a one sample t-test to compare the mean SUS score at T1 to the threshold score of 71 indicative of "good" usability. If the distributions of SUS scores suggest asymmetry or nonnormality, the non-parametric sign test (highly asymmetrical) or Wilcoxon signed-rank test (non-normality) will be performed in lieu of one-sample t-tests. To assess whether there was a significant improvement in the continuous secondary cognitive/behavioral outcomes from baseline to end of study (T₀ to T₁), we will perform two-sided paired t-tests on the pairwise differences. If any of the distributions of pairwise differences suggest asymmetry or nonnormality, the non-parametric Wilcoxon signed-rank sum test will be performed in lieu of paired t-tests. We will use the McNemar's test for to compare paired proportions.

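### The SUS question is set as a mean against 71, but skewed or non-normal scores switch it to a test of a median or pseudo-median, which can give a wrong answer about the mean

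*Combined protocol and SAP*

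**What the plan says.** Section 5.0 (Data Collection and Outcome Measures) lists three primary outcomes, the first being "ease of use and satisfaction as assessed by the System Usability Scale". Section 6.0 plans a one-sample t-test to "compare the mean SUS score at T1 to the threshold score of 71", the value it takes as marking good usability.

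The trigger for leaving the t-test is: "If the distributions of SUS scores suggest asymmetry or nonnormality". In that event, "the non-parametric sign test (highly asymmetrical) or Wilcoxon signed-rank test (non-normality) will be performed in lieu of one-sample t-tests". The section names no diagnostic or cut-off for either branch. It does not say that the quantity of interest changes, or which estimate and interval go with the replacement test.

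For the secondary pre/post outcomes the same section has one fallback for both asymmetry and non-normality: "the non-parametric Wilcoxon signed-rank sum test will be performed in lieu of paired t-tests". No sign test is offered there.

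**The concern.** The three tests answer three questions:

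- t-test: is the mean different from 71?
- sign test: is the median different from 71?
- Wilcoxon signed-rank test: is the pseudo-median (the median of averages of pairs of scores) different from 71?

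The answers agree when the distribution is symmetric. The plan leaves the t-test partly because of asymmetry, which is the condition under which they part. With left skew the median and pseudo-median lie above the mean, so the replacement test can favour 'above 71' when the true mean is not above it. With right skew the error runs the other way.

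A significant sign test is a correct statement about the median. The mistake would be to report it as the answer to a question posed about the mean. Because the switch depends on how the observed scores look, the quantity tested is settled only after the data are seen.

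At stake is the study's one inferential statement on a primary outcome: whether usability is reported as good. The user-experience items and the interviews are not affected.

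**Working it through.** **Inputs.** From section 6.0: target (mean), threshold (71) and the three candidate tests. The documents do not give the sample size, SUS SD, alpha, expected shape or a switching cut-off. Two-sidedness is stated only for the secondary outcomes ("we will perform two-sided paired t-tests on the pairwise differences"). There is no planned figure to reproduce, and everything below rests on assumed values.

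**Step 1: one dataset, different answers.**

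*Example A*, constructed, n = 50: mean 70.05, SD 15.5, median 75, skewness −1.3, 36 scores above 71 and 14 below.

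- t = (70.05 − 71) / (15.5/√50) = −0.95 / 2.19 = −0.43, p = 0.67; 95% CI for the mean 65.6 to 74.5 (percentile bootstrap 65.6 to 74.1).
- Exact sign test, 36 of 50: p = 0.003, above 71.
- Wilcoxon: p = 0.24.

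*Example B*, constructed, n = 60: 14 scores of 77.5, 10 of 80, 10 of 82.5, 6 of 85, 8 of 30, 6 of 35, 6 of 40.

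- Mean = (1085 + 800 + 825 + 510 + 240 + 210 + 240)/60 = 3910/60 = 65.2; median 77.5; skewness −0.71.
- t-test: t = −2.04, p = 0.045, so the mean is *below* 71.
- Sign test, 40 of 60: p = 0.013, so the median is *above* 71.
- Wilcoxon: p = 0.48.

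**Step 2: each test applied throughout, with no switching.** True mean about 71, scores on the 2.5-point grid, n = 30 to 100, two-sided 5% (nominal 2.5% on the upper side), 4,000 samples per setting. Percentage significant above 71:

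| Shape | t-test | Wilcoxon | Sign |
|---|---|---|---|
| Beta, SD 20, skewness −0.68 | 2.6–3.7 | 6.7–11.6 | 8.1–16.5 |
| Beta, SD 25, skewness −0.78 | 3.2–3.7 | 6.6–13.3 | 12.1–29.4 |
| 80/20 mixture, skewness −1.19 | 3.3–5.7 | 20–47 | 44–91 |

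The sign and Wilcoxon rates are higher at n = 100 than at n = 30 because a larger sample detects the shifted target more surely. In the last row 66.7% of scores exceed 71, so at n = 100 the sign test's expected statistic is about (0.667 − 0.5)/(0.5/√100) = 3.3.

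**Step 3: the switch itself.** Assumed rule: if Shapiro-Wilk p < 0.05, use the sign test when |skewness| > 1 and Wilcoxon otherwise; if not, keep the t-test. True mean exactly 71, 10,000 replicates per cell. Percentage of studies declaring above 71:

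| Shape | n=30 | n=50 | n=80 | n=100 | t-test alone |
|---|---|---|---|---|---|
| Mixture, SD 15.6, skewness −0.70 | 8.7 | 11.6 | 15.2 | 17.6 | 3.2–4.0 |
| Beta, SD 18, skewness −0.63 | 6.2 | 8.5 | 10.6 | 11.3 | 3.1–3.7 |

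The mixture is 80% normal (77, SD 10) and 20% normal (47, SD 10), capped at 0 to 100 and shifted to mean 71.

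**Step 4: other rules and shapes.**

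- Sign test from |skewness| > 0.5: 10–28% (mixture) and 7–13% (beta).
- Most favourable reading (Wilcoxon only if |skewness| ≤ 0.5, t-test kept from 0.5 to 1): 6–8% and 4–6%.
- Symmetric scores: 2.2–2.5%, no inflation.
- Right skew (mixture mirrored): above 71 falls to 0.6–1.3%, and below 71 rises to 6–9%, against about 3% for the t-test.

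**The case against.** Naming non-parametric fallbacks in advance is conventional. The pairing also has a logic: Wilcoxon where symmetry is tolerable, the sign test where it is not. A median can be a legitimate target for a bounded, skewed score. Descriptive statistics are planned for the survey data, so a reader would probably see an SUS summary beside the p-value. This is a usability study ahead of a separately proposed trial, and no stated decision depends on the SUS test.

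The size also rests wholly on assumed shapes and rules. Under the step 3 rule, the sign test is chosen in only 5–14% of mixture studies and 2–9% of beta studies. An outright clash, with the selected test significant above 71 while the *observed* mean is at or below 71, occurs in about 0.5% of studies or fewer. Example B, at skewness −0.71, would go to Wilcoxon under that rule and so would not be declared above 71. In example A only the sign test conflicts with the t-test.

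Much of this stands. Visible contradictions within one dataset should be rare under moderate skew, no likely figure for this study can be given, and naming the median in advance would be a valid alternative repair. None of it removes the mismatch. The plan asks about the mean, replaces the test of the mean, and never restates the target. If Wilcoxon is kept for roughly symmetric scores, it does agree with the mean, but moderate asymmetry then has no assigned test. The pre/post rule in the same section sends asymmetric data to Wilcoxon, so that reading is not applied consistently. The planned descriptive statistics do not name a mean with a confidence interval as the reported result.

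**Conclusion.** The concern holds. Followed as written, the rule can give a wrong answer about the mean on the only hypothesis test stated for a primary outcome. That the tests have different targets follows from the text alone.

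The size depends on assumptions. With a true mean of 71, moderate left skew (about −0.6 to −0.7) and n = 30 to 100, false declarations above 71 run from about 4% under the most favourable reading to 28% under the least, against a nominal 2.5%. The t-test stays at 3.1–4.0% for the same two shapes, so the switch is not needed there to protect the test of the mean. With symmetric scores there is no harm. The main risk lies in the sign-test branch, which the plan assigns to the most skewed data. This should be fixed, though it bears on how one result is interpreted and not on the conduct of the study.

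**What to change.** Keep the mean as the target whatever the distribution, and drop the replacement clause for SUS in section 6.0. Suggested wording:

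> We will report mean SUS at T1 with a 95% confidence interval and test it against 71 with a one-sample t-test. If scores are skewed, we will add a bootstrap 95% confidence interval for the mean. The median, the percentage scoring above 71, and the sign and Wilcoxon results will be reported as sensitivity analyses, each labelled with the quantity it tests.

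If the team prefers the median, it should be named as the target before the scores are seen, with its own estimate and interval, and the test should not switch.

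The cost is one or two sentences and no new data. Every test now named is retained. The downside is a slightly wider interval when scores are heavy-tailed.

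### Does McNemar's test leave the stage-of-change items without a usable pre/post analysis because no cut-point is named?

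*Combined protocol and SAP*

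**What the plan says.** Section 5.0 Study Procedures, Table 1, lists nine secondary outcomes measured at T0 and T1. Seven are typed continuous and two categorical. The categorical ones are the knowledge-of-measures items ("Unique study specific items to assess participants' knowledge of measures of diabetes health status") and the readiness items ("Four items assessment resources to assess stage of change based on the Transtheoretical Model (TTM) of behavior change"). The readiness items cover physical activity, medication management, glucose self-monitoring and diet. Table 1 gives no response options or number of stages for them.

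The text above Table 1 says the pre/post changes are assessed "to estimate effect size and standard deviations for power analyses necessary to plan a subsequent randomized controlled trial".

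Section 6.0 Statistical Analysis Plan has three sentences that bear on this:

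- a general one, "We will use descriptive statistics to characterize the study participants and survey data";
- one for the continuous outcomes, which begins "To assess whether there was a significant improvement in the continuous secondary cognitive/behavioral outcomes from baseline to end of study" and continues "we will perform two-sided paired t-tests on the pairwise differences", followed by a Wilcoxon fallback;
- one for paired categorical data, "We will use the McNemar's test for to compare paired proportions".

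No cut-point, collapsing rule or ordinal paired method appears anywhere.

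**The concern.** The t-test and Wilcoxon rule stops at the continuous outcomes, so McNemar's test is the only inferential method left for the two categorical ones. It suits knowledge items scored right or wrong. A stage-of-change item suggests several ordered stages, and McNemar's test can be applied to it only after the stages are split in two. Each possible split counts a different set of discordant pairs. A participant who moves without crossing the split is counted as unchanged.

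Two things would then be at stake. First, the effect size carried into planning the later randomized trial could reflect where the split was put as much as how far participants moved. Second, an analyst who chose the split after seeing the T1 data would have several chances at a small p-value. If the items are instead only to be described, the plan states no specific method for estimating their change.

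**Working it through.** **Reproducing a stated figure.** There is none. The documents give no sample size, stage count, baseline distribution or expected movement for this outcome. Everything below is an illustration on assumed inputs.

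**Dependence on the cut.** Assume five ordered stages and single-stage moves, with 30% of those who can move up doing so and 10% of those who can move down doing so. For the cut between stages k and k+1, with baseline proportions p:

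- up-crossers = 0.30 × p(k)
- down-crossers = 0.10 × p(k+1)
- net change = up-crossers minus down-crossers

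Power is for n = 80 (assumed), two-sided 5%, by binomial summation over the number of discordant pairs. It is shown for the uncorrected chi-square version and, in brackets, the exact version.

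Scenario 1, baseline 15/20/25/15/25%:

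| Cut | Up (%) | Down (%) | Net (points) | McNemar power |
|---|---|---|---|---|
| 1\|2 | 4.5 | 2.0 | +2.5 | 0.13 (0.04) |
| 2\|3 | 6.0 | 2.5 | +3.5 | 0.17 (0.09) |
| 3\|4 | 7.5 | 1.5 | +6.0 | 0.44 (0.28) |
| 4\|5 | 4.5 | 2.5 | +2.0 | 0.09 (0.03) |

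Scenario 2, baseline 5/10/50/10/25%:

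| Cut | Up (%) | Down (%) | Net (points) | McNemar power |
|---|---|---|---|---|
| 1\|2 | 1.5 | 1.0 | +0.5 | 0.02 (0.00) |
| 2\|3 | 3.0 | 5.0 | -2.0 | 0.09 (0.03) |
| 3\|4 | 15.0 | 1.0 | +14.0 | 0.95 (0.91) |
| 4\|5 | 3.0 | 2.5 | +0.5 | 0.05 (0.01) |

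The estimate does move with the cut. The reversal of sign needs the uneven baseline of scenario 2, with half the participants in one middle stage. In scenario 1 every cut points the same way.

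**A sign test on direction as the alternative.** All movers count.

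- Scenario 1: up 0.30 × 75% = 22.5%, down 0.10 × 85% = 8.5%. Power is 0.64 (0.55 exact), above every cut.
- Scenario 2: up 22.5%, down 0.10 × 95% = 9.5%. Power is 0.56 (0.46 exact), well below the best cut at 0.95 (0.91 exact).

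Neither approach is uniformly better.

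**A second assumed table.** Take 60 pairs, five stages, T0 counts 10/12/13/9/16 and T1 counts 5/10/16/13/16. From the first cut to the last, the up and down crossers are 6 and 1, 8 and 1, 6 and 2, 3 and 3. Net changes are 5/60 = +8.3, 7/60 = +11.7, 4/60 = +6.7 and 0 points. Exact p-values are 0.125, 0.039, 0.289 and 1.0. The pattern is the same: dependence on the cut, of a size set by the assumed table.

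**Choosing the cut after the fact.** Assume no net movement, n = 80, and 15% or 20% moving each way. The chance that at least one cut gives p < 0.05 was simulated with 40,000 studies per setting:

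| Baseline stages | Three stages | Four | Five |
|---|---|---|---|
| Drawn at random, equal probability; chi-square McNemar | about 9% | about 13% | 17% to 18% |
| Fixed equal numbers per stage; chi-square McNemar | 5% to 6% | 8% to 10% | 11% to 13% |

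The exact test gives about 3% to 6% with random baselines and below 3% with fixed ones. The inflation therefore belongs largely to the chi-square version, and the plan does not say which version is meant.

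**The case for a change.** The strongest case for a change is that the gap is real and would take a sentence or two to close. Stages become a proportion only through a cut, and changing the cut changes the quantity estimated, whatever numbers are assumed. Section 5.0 introduces the whole secondary list as input to power calculations, and a general sentence on descriptive statistics does not define an effect size. On either reading of section 6.0, something is left unwritten for these four items.

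That much stands. Several links beyond it are weaker:

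- Section 6.0 does not assign McNemar's test to the readiness items. It speaks only of paired proportions.
- More than two stages is a fair inference from the name of the measure, but it is not stated. With two recorded categories no cut would be needed.
- The items are survey data, for which descriptive statistics are planned. A T0-by-T1 stage table, or a change in the percentage at a given stage, fits that sentence and is an estimate of change.
- The stated planning use mentions standard deviations, which fit the seven continuous outcomes most naturally. Nothing says the later trial, which is to be proposed separately, will be powered on readiness to change.
- The obvious replacement is a trade-off. A sign test ignores how far a participant moves, cannot register forward movement from the top stage, and in scenario 2 has power 0.56 against 0.95 for the best cut.

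**Conclusion.** No change to the plan is called for. What remains is an unwritten detail, the cut or the ordinal method for four items forming one secondary outcome. A competent analyst fills it with a stage table, a conventional dichotomy or a paired ordinal test. None of these gives an unsound result when reported for what it is, and the calculations do not favour one over the others throughout.

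The general statement holds: if the items have more than two stages and McNemar's test is applied to them, the estimate can depend on the cut. How much cannot be derived from the documents. The ranges of +2.0 to +6.0 and -2.0 to +14.0 points rest wholly on the assumed stages, baselines and movement rates. The post hoc risk also depends on the version of the test and is small to absent with the exact one. The primary outcomes (System Usability Scale, usage and user experience) and the seven continuous secondary outcomes are untouched, and no decision within this study is tied to the readiness items.
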